According to a review by Neal et al., the study of vitamin D levels and stress fracture occurrences is a relatively new topic.¹ The best understood data comes from studies on military recruits, due to their rapid increase in activity and musculoskeletal stress. However, there is much less data regarding the effects of vitamin D levels on stress fracture occurrences in conditioned athletes.¹ Furthermore, since levels of vitamin D have been shown to vary with season and sunlight exposure, this leads to the idea that indoor sports and winter seasons may at a higher risk for stress fractures. One study by Valimaki et al.(need reference number here) showed a significant increase in vitamin D levels in Finnish men over a period of 6 months. First measurements in July listed only 0.9% of their subjects having levels below 20 nM/L, while in the winter the number of subjects in the deficient range increased to 38.9%.⁴ These findings support the idea that vitamin D levels are different at various seasons of the year.

As mentioned, there are several studies on vitamin D levels and/or calcium levels and their relationship with bone health. One study by Lappe et al. examined this relationship in female navy recruits by running a double-blind study, giving vitamin D and calcium supplementation to half of the subjects and a placebo to the other half.⁴ There were 3700 recruits that finished the study, and 309 recruits were diagnosed with at least one stress fracture. From the data, their results concluded that group with supplementation showed a decrease in stress fracture occurrence by roughly 21% compared to the control group.⁵ This significant decrease shows that supplementation of both vitamin D and calcium benefited in maintaining adequate bone health. The study also showed a reversal in bone mineral content. They found that vitamin D and calcium supplementation not only stopped bone mineral loss, but also began increasing total content by 2-3%.

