Other than normal activities required for each sport, the main risk to each subject primarily involves taking blood samples. Although sampling is routine, there will still be risks of bleeding, bruising, dizziness, and possible infections. Allowing only trained individuals to take blood samples will minimize these risks. Any injury that occurs during a sports event or training activity will be handled accordingly by one of the physicians or athletic trainers on site. All injuries, regardless of nature, will be recorded per subject.

Blood samples will be tested for 25(OH) vitamin D levels using the order (Vitamin D 25-OH, Calcifediol Request). The data will be kept for each subject, day of recording, and level on an Excel spreadsheet. Any stress fracture reported will be listed on the same spreadsheet, along with the date of occurrence and severity, per subject.

Each team's athletic training staff will administer one vitamin D capsule to each team member once a week before a scheduled meeting or practice. This will help ensure every athlete takes the proper dosage, no dosages are skipped, and every week is accounted for. Athletes may still have decreased levels after the first course, and a second round of 8-week treatment will be administered. Should the second round of treatment fail to elevate vitamin D levels, the January test will confirm and treatment will continue. As many students leave to visit family during break, it will be rather difficult to monitor every athlete's levels during this timeframe.

Retrospective: The retrospective portion of the study will involve review of athletes of the same sports teams and inclusion/exclusion criteria from seasons up to four years ago. Review of previous athlete information will be drawn from electronic records kept by the athletic training staff, both electronic and hand-written records kept by the orthopedic staff, and any lab records retained at Palmetto Health. The information that will be obtained will include athlete demographics, their respective sports, stress fracture occurrences, and vitamin D levels if this was noted. The time period for the retrospective chart review will be from January 2010 through August 2015. The rate of stress fracture occurrence will be compared to the prospective treatment phase. It is important to note that individuals in the retrospective analysis will not have personal information reported, as the main purpose is to determine a baseline stress fracture rate.

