Analysis of the historic group will follow similar protocol as the recruitment of new subjects. Information from previous subjects will include including gender, age and sports team information. Additional information obtained will include stress fracture occurrence(s) and location, and vitamin D levels (if recorded).

h) Data and Specimen Banking

Data for each enrolled subject will consist of name, age, gender, ethnicity, and sports team. Any personal or private information collected will only be used during data analysis. This may contain information regarding menstruation, dietary habits, and previous pregnancies. Names and private information of subjects will not be released outside of personnel directly attached to the study, and they will not be included in the final study publication. Serum 25(OH) vitamin D levels for each subject will be recorded at the initial examination and 8 weeks following the beginning of treatment. Every injury diagnosis will be recorded per individual. There will be no blood sample banking after vitamin D levels are determined.

i) Statistical Analysis

Sample Size Justification

A power analysis was performed using PASS 2008 software on the research aim to compare the proportion of athletes that experience a stress fracture in those with normal vitamin D levels (either normal at baseline or treated by supplementation) compared to four previous years when this approach was not used. You can see that if the proportion of athletes experiencing stress fracture in the control group is 10%, then if the true reduction in the treated group was to 4% or less, we would have greater than 80% chance (power) in this study to achieve statistical significance in a test of the two proportions.

Two Independent Proportions (Null Case) Power Analysis

Numeric Results of Tests Based on the Difference: P1 - P2

H0: P1-P2=0. H1: P1-P2=D1<>0. Test Statistic: Z test with pooled variance

Power	Sample	Sample	Prop H1	Prop	Diff if H0	Diff if H1	Target Alpha
	Size Grp 1	Size Grp 2	Grp 1 or Trtmnt	Grp 2 or Control			
	N1	N2	P1	P2	D0	D1	
0.9946	200	800	0.0200	0.1000	0.0000	-0.0800	0.0500
0.9509	200	800	0.0300	0.1000	0.0000	-0.0700	0.0500
0.8220	200	800	0.0400	0.1000	0.0000	-0.0600	0.0500
0.6188	200	800	0.0500	0.1000	0.0000	-0.0500	0.0500
0.4048	200	800	0.0600	0.1000	0.0000	-0.0400	0.0500
0.2337	200	800	0.0700	0.1000	0.0000	-0.0300	0.0500
0.1224	200	800	0.0800	0.1000	0.0000	-0.0200	0.0500

Statistical Analyses

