1. To compare the proportions of student athletes experiencing stress fractures during the 2015-15 academic year with the four previous years.

A large sample test of the difference in two independent proportions will be carried out, along with computation of 95% confidence interval on the difference between the two proportions. An exploratory logistic regression model will be built with stress fracture as the outcome, group (2015-16 versus the previous four years) as the major predictor variable and type of sport and gender as covariates.

2. To compare the proportions of 2015-16 academic year student athletes experiencing stress fractures in the vitamin D insufficient or deficient group and the group with vitamin D levels ≥ 30 ng/mL.

A large sample test of the difference in two independent proportions will be carried out, along with computation of 95% confidence interval on the difference between the two proportions. An exploratory logistic regression model will be built with stress fracture as the outcome, group (baseline vitamin D deficient versus normal baseline vitamin D level) as the major predictor variable and type of sport and gender as covariates.

3. In 2015-16 athletes, to explore associations between the TRIAD questionnaire risk factors and low baseline vitamin D levels.

Exploratory descriptive and inferential statistics will be carried out, including the building of linear and logistic regression models, looking for an association between the questionnaire items and baseline vitamin D levels (continuous and dichotomized).

4. In 2015-16 athletes, to explore associations between the TRIAD questionnaire risk factors and subsequent stress fractures.

Exploratory descriptive and inferential statistics will be carried out, including the building of logistic regression models, looking for an association between the questionnaire items and the subsequent occurrence of a stress fracture.

j) Data Management

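### Age is listed for both periods but left out of the Aim 1 logistic model without a reason; adding it is a free, minor improvement

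*Combined protocol and SAP*

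**What the plan says.** Aim 1 compares the 2015-16 athletes with athletes on the same teams in earlier years. Section i, Statistical Analyses, item 1, names two analyses.

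- The main one is unadjusted: "A large sample test of the difference in two independent proportions will be carried out", with a 95% confidence interval.
- The second is a model: "An exploratory logistic regression model will be built with stress fracture as the outcome", and with "group (2015-16 versus the previous four years) as the major predictor variable and type of sport and gender as covariates".

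Two sections say which athlete characteristics will be available.

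- Historical athletes (section g, Retrospective): "Information from previous subjects will include including gender, age and sports team information". The same section also says, more loosely, "The information that will be obtained will include athlete demographics, their respective sports, stress fracture occurrences, and vitamin D levels if this was noted".
- 2015-16 athletes (section h, Data and Specimen Banking): "Data for each enrolled subject will consist of name, age, gender, ethnicity, and sports team".

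Age, gender and sports team are therefore named explicitly for both periods. The model uses the last two. The documents do not explain why age is left out, and they plan no matching, stratification or sensitivity analysis by age.

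**The concern.** The Aim 1 groups are formed by calendar year, not by randomisation. The logistic model is the plan's only means of asking whether a difference between the periods reflects who was on the teams. If the age mix differs between the periods and fracture risk varies with age, the part not carried by sport or gender remains in the period coefficient. It could make the 2015-16 result look somewhat better or somewhat worse than it is.

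There is some reason in the document to think of age. The Background says the military data are the best understood "due to their rapid increase in activity and musculoskeletal stress", which makes a recent rise in training load a plausible risk factor. Age is the only characteristic named for both periods that says anything about how long an athlete has been in collegiate training.

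**Working it through.** **1. The plan's own figure.** Sample Size Justification gives N1 = 200, N2 = 800, P1 = 0.04, P2 = 0.10, two-sided alpha 0.05, pooled Z test, power 0.8220.

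- Pooled proportion: (200 × 0.04 + 800 × 0.10) / 1000 = 0.088.
- SE under H0: √[0.088 × 0.912 × (1/200 + 1/800)] = 0.02240.
- SE under H1: √[0.04 × 0.96/200 + 0.10 × 0.90/800] = 0.01745.
- Power: Φ[(0.06 − 1.96 × 0.02240) / 0.01745] = Φ(0.92) = 0.822.

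The figure reproduces. It belongs to the unadjusted test, so adding age to the model does not change it.

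**2. How far an age shift could move the crude difference.** The documents give only the 10% control rate. The rest is assumed: a share s0 of younger or newer athletes in the control years, a share s1 in 2015-16, a risk ratio R for those athletes against the others, and no treatment effect.

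- Rate in the other athletes: b = 0.10 / [1 + s0(R − 1)].
- Expected 2015-16 rate: b × [1 + s1(R − 1)].
- Distortion: 0.10 × (s1 − s0)(R − 1) / [1 + s0(R − 1)].

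| R | s0 | Shift (points) | Distortion (percentage points) |
|---|---|---|---|
| 1.5 | 25% | ±5 | 0.10 × 0.05 × 0.5 / 1.125 = ±0.22 |
| 2 | 30% | ±10 | 0.10 × 0.10 × 1 / 1.30 = ±0.77 |
| 2 | 25% | ±10 | 0.10 × 0.10 × 1 / 1.25 = ±0.80 |
| 2 | 25% | ±15 | 0.10 × 0.15 × 1 / 1.25 = ±1.20 |

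The range is about 0.2 to 1.2 points, against a planned difference of 6. A deliberately extreme case (R = 3, s0 = 25%, shift 20 points) gives 0.10 × 0.20 × 2 / 1.5 = 2.7 points, still less than half of 6.

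**3. The same on the model's scale.** A fall in the share from 30% to 20% with R = 2 gives 9.23% against 10%. The crude odds ratio is (0.0923/0.9077) / (0.10/0.90) = 0.92. A rise from 25% to 35% gives 10.8% and an odds ratio of 1.09. The planned effect, 4% against 10%, is an odds ratio of 0.375. If the shift were even across sports and genders, adjusting for those two would leave roughly 0.92 or 1.09 in the period term.

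**4. What it would do to the crude test.** This shows scale only.

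- Exact enumeration at 200 v 800 for 9.23% v 10%: the two-sided rejection rate goes from 0.050 to 0.056. Within that, the false-benefit side rises from 0.021 to 0.044 and the false-harm side falls to 0.012.
- Power for a true 60% reduction when the untreated rate is 10.8% (0.4 × 10.8% = 4.32% v 10%): 0.762 instead of 0.822 by the plan's formula, or 0.774 instead of 0.831 by exact enumeration.

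**5. Whether the model can carry another term.** Expected fractures at the planning rates are 800 × 0.10 = 80 historical, plus 200 × 0.04 = 8 to 200 × 0.10 = 20 in 2015-16, so 88 to 100 in all. Slopes are period, three for four sports, gender and a linear age term, six in total. That gives 88/6 = 14.7 to 100/6 = 16.7 events per slope.

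**The case against.** The strongest case on the other side has five parts.

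- **The model is exploratory.** Its wording does not bar adding age later, and choosing sport and gender breaks no rule in the plan. This stands, and it is why the point is an improvement and not an error. Naming age in advance still has value, because it stops the term being added or dropped once results are seen.
- **The fix does not touch the main test.** A reader might infer from the rejection rates and power above that adding age would repair them. It would not: they describe the unadjusted comparison, which stays as it is.
- **The groups may not differ in age at all.** A reader might take 2015-16 as one intake set against four. The documents do not support that. Section a hopes to enrol every player on the teams, section g expects returning athletes among them, and the controls come from the same teams under the same criteria. Both groups mix new and returning athletes, and no passage reports a shift. Some difference is still possible, because 2015-16 athletes enter by consent and historical athletes come from records.
- **The link between age and risk is not stated.** The Background contrasts military recruits with conditioned athletes and places collegiate athletes on the conditioned side. It does not say that younger or first-year athletes fracture more. The risk ratios used here are assumptions.
- **Age is not experience.** Neither list names class year or years on the team, so an age term may remove only part of a new-versus-returning difference.

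It would also go too far to call age the only possible shared variable left out. The historical demographics are undefined and might include ethnicity, and vitamin D is shared where it was noted. What holds is that, of the three characteristics named explicitly for both periods, age is the one not used.

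**Conclusion.** The point holds in a limited form. Age is listed for both periods, the Aim 1 model omits it, and no reason is given. In a non-randomised comparison of years, a difference in age mix would stay in the adjusted period estimate to the extent that sport and gender do not capture it.

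The size is unknown from the documents. For assumed risk ratios of 1.5 to 2 and share shifts of 5 to 15 points, the crude difference moves by about 0.2 to 1.2 percentage points in either direction. A reader might infer that age mix could by itself pass for the planned benefit or hide it. The figures do not support that: the distortion is at most a fifth of the planned 6 points (1.2/6 = 0.20), and in the masking example power is still about 0.76. Severity is minor.

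**What to change.** In section i, Statistical Analyses, item 1, prespecify age at the start of the season as a covariate in the logistic model, beside type of sport and gender, and tabulate age by period. If the investigators prefer to leave age out, a sentence giving the reason would do. The text should say that age stands in for time in collegiate training and may not capture it fully.

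The cost is one model term and one table, with no new data. The two-proportion test and its stated power stay as they are. The change is proposed for Aim 1 only. The Aim 2 model also omits age, but it rests on the 2015-16 fractures alone, about 8 to 20 at the planning rates, which is already few for group, three sport terms and gender.

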Any subject that has consented and meets inclusion/exclusion criteria will be tested for serum vitamin D levels, and those individuals showing deficiency will be provided supplemental treatment in order to raise vitamin D levels to normal ranges. Individuals who do not show deficiency levels will be included in the study, but will not receive any treatment. These subjects will be added to an additional control group. There will be no payment for enrollment in the study.

b) Inclusion/Exclusion Criteria

Each individual who has given consent will have blood work tested. Should serum vitamin D levels be lower than 30 ng/mL, they will be included in the treatment group. Subjects with normal ranges will be included in the prospective control group. Both male and female athletes will be eligible to enroll. Any individual who currently has a stress fracture or is in the stage of recovering from a lower extremity musculoskeletal injury will be excluded from the study. Questionnaires will be provided in order to gather an understanding of diet, exercise regimen, and related lifestyle questions. Specifically, there will be a question regarding current vitamin D or other multivitamin supplement currently being taken, what the dosage is, and how often it is taken. Female athletes will be provided a separate questionnaire in regards to individual dietary habits and menstrual cycle.

c) Local Number of Subjects

The number of subjects in the study will be based on the number of individuals meeting the inclusion/exclusion criteria and provide written consent. They will be drawn from men's basketball, soccer, and track/field, and women's basketball, soccer, track/field, and cross-country. There will be no cutoff to the number of individuals accepted. Tentatively, there will be roughly 200 athletes enrolled in the study.

d) Study-Wide Number of Subjects

The number of subjects in the prospective portion of the study will be the number of qualified enrollees. This number may change, depending on the length of the study. Should it be necessary to extend the timeline, the study will enroll new subjects for the second season, but will still include them in the test group.

e) Study Timelines

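### Aim 1 sets one season against four pooled seasons with binomial error only, so the plan cannot separate a season effect or trend from supplementation

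*Combined protocol and SAP*

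**What the plan says.** Item 1 of Statistical Analyses in the combined protocol and SAP plans a large-sample test of two independent proportions, with a 95% CI for the difference. It adds an exploratory logistic model in which period is binary, "group (2015-16 versus the previous four years", with sport and gender as covariates. No section provides a year term, a trend check, a between-season variance or a year-by-year display.

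Sample Size Justification treats the comparison as 200 against 800 independent athletes. The hypotheses are two-sided, "H0: P1-P2=0. H1: P1-P2=D1<>0", and the test is specified as "Test Statistic: Z test with pooled variance". The key row of the power table reads "0.8220 200 800 0.0400 0.1000 0.0000 -0.0600 0.0500". The prospective size is tentative: "Tentatively, there will be roughly 200 athletes enrolled in the study".

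On the historical data, the Retrospective part of Procedures Involved says that "the main purpose is to determine a baseline stress fracture rate". The Setting section goes further: the earlier, untreated seasons are the control by which an effect of treatment on fracture occurrence is to be judged.

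The control period is not stated consistently. Specific Aims gives five previous years. Sample Size Justification and Statistical Analyses give four. The Retrospective text says up to four years, but sets a chart-review window of January 2010 to August 2015, which spans five full academic years and part of a sixth.

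**The concern.** There is one season under the new approach, so supplementation and calendar year coincide. Training load, staffing, schedules and injury reporting may all differ between 2015-16 and earlier years, and the planned comparison credits any such difference to the period term. Sport and gender adjustment removes only shifts in that mix, and only in an exploratory model. One difference between periods is visible in the documents: 2015-16 complaints are examined prospectively by a physician, while earlier fractures come from existing records. More complete detection in 2015-16 would work against a benefit, so the bias need not favour supplementation.

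The standard error reflects only athlete-to-athlete binomial variation. If seasons also differ among themselves, the 2015-16 proportion carries a season deviation that appears nowhere in the interval. A downward trend before 2015 would look like benefit; an upward one would hide it. At stake is whether the Aim 1 p-value and CI can support a statement about supplementation.

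**Working it through.** **Inputs from the documents.** N1 = 200, N2 = 800, control rate 10%, treated rate 4%, two-sided alpha 0.05, pooled-variance Z test (Sample Size Justification). Reading 800 as 4 seasons × 200 is an inference.

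**Input not in the documents.** The between-season SD of the true rate, τ. A range of 0 to 3 percentage points is assumed.

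**1. The plan's own power.**
- Pooled rate: (200×0.04 + 800×0.10)/1000 = 0.088.
- Null SE: √[0.088×0.912×(1/200 + 1/800)] = 0.02240.
- Alternative SE: √[0.04×0.96/200 + 0.10×0.90/800] = 0.01745.
- Power: Φ[(0.06 − 1.96×0.02240)/0.01745] = Φ(0.923) = 0.822.

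This matches the stated 0.8220. The arithmetic is right; it rests on binomial error alone.

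**2. Variance with a season component, no treatment effect.**
- Binomial part: 0.10×0.90×(1/200 + 1/800) = 0.0005625, so SE = 2.37 points.
- Added part: τ²×(1 + 1/4), less τ²×(1/200 + 1/800), that is 1.24375τ². The new season contributes τ² and the four control seasons together only τ²/4.
- Variance ratio: 1 + 1.24375τ²/0.0005625.
- Approximate type I error: 2[1 − Φ(1.96/√ratio)].

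The last two columns are from simulation: beta-distributed season rates with mean 10%, 200 athletes per season, four control seasons, the planned test, 400,000 replicates.

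| τ (points) | Variance ratio | Type I, formula | Type I, simulated | False benefit, simulated |
|---|---|---|---|---|
| 0 | 1.00 | 5.0% | 5.0% | 2.1% |
| 1 | 1.22 | 7.6% | 7.5% | 3.3% |
| 2 | 1.88 | 15.3% | 15% | 6.9% |
| 3 | 2.99 | 25.7% | 25% | 12% |

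A fifth control year hardly changes this (15% at τ = 2), because the single new season carries most of the added variance.

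**3. A linear trend, no treatment effect, no random season variation.** The mean control year lies 2.5 years before 2015-16. With a control mean of 10%, a decline of 1 point per year puts 2015-16 at 10 − 2.5 = 7.5%, and the planned test rejects about 17% of the time. That sits between the plan's own power figures of 0.2337 at 7% and 0.1224 at 8%. At 2 points per year the expected rate is 5% and rejection is about 63%.

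**4. What season-level analyses can deliver.** For a 60% relative reduction (10% to 4%), a t test of one new season against four or five earlier ones has about 34%-50% power at τ = 0-1 and 13%-26% at τ = 2-3. With four control years, a heterogeneity test has 9%, 24% and 45% power at τ = 1, 2 and 3, and a trend of 1 point per year is detected about 18% of the time. A linear-trend-adjusted contrast has about 42%-53% power at 4%, depending on the variance form, and its type I error under random season variation stays near 7.6%, 15% and 25%.

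**The case against.** The strongest reply is that the problem is conditional. With no season variation the planned test has 5% type I error and its interval is correct, and the documents give no figure showing otherwise. That stands. A reader might infer that ordinary season variation will be reported as a supplementation effect, or that the interval is too narrow as it is. The documents support neither: they show only that the plan could not tell the difference if such variation exists.

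Second, the two-sided error rates overstate the specific harm of a false benefit, which is roughly half as frequent. That also stands, and both are given.

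Third, the extra analyses are weak, and the trend-adjusted contrast does not repair random season variation. This is why they cannot replace the pooled test. A reader might go on to require that any drop persist in them before it is credited to supplementation. That would turn low-powered analyses into a gate that a true fall to 4% would often fail. Even a drop that passed could reflect some change peculiar to 2015-16.

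Fourth, sport and gender are adjusted for, and a further season is allowed. The adjustment does not touch calendar effects. The extension is triggered by too few data points, and the Aim 1 analysis still names 2015-16 only.

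**Conclusion.** The point holds in conditional form. Nothing in the plan separates a season effect or trend from supplementation, yet the comparison is given a causal purpose. If the between-season SD is 1 to 3 points, two-sided type I error is about 7.6% to 25%, and false benefit about 3.3% to 12% rather than about 2%. These figures assume a 10% control rate, 200 athletes in every season, independent athletes and a season SD that is not in the documents. The design effect is only 6 points, so modest season variation matters.

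A reader might also infer that the sample size calculation is wrong. It is not: it reproduces exactly under its stated model. The pooled test can stay, but its p-value and CI cannot by themselves carry the conclusion that supplementation lowered the rate. This is a change the plan should make; it does not invalidate the design.

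**What to change.** - Keep the pooled two-proportion test and CI.
- Record academic year for each historical athlete. The listed extraction items do not name it, although the text on reviewing past seasons implies it.
- Report the fracture rate with a CI for each academic year.
- Prespecify one season-level sensitivity analysis: a random-season or overdispersion-scaled interval for 2015-16 against the earlier seasons. Give a calendar-trend-adjusted estimate as descriptive support only.
- State that a non-significant heterogeneity or trend test is not evidence of stability.
- Describe Aim 1 as a before-after association, not as proof that supplementation caused a drop. Set no rule that attribution depends on the supporting analyses.
- Reconcile the control period across Specific Aims, the Retrospective text, Sample Size Justification and Statistical Analyses.

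The cost is one more extracted item, a little analysis and a wider supporting interval. Given the power in step 4 of the working, that interval should stay secondary. No new subjects are needed.

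### At the 4% design rate, the exploratory Aim 2 logistic model has about 1.6 fractures per slope and no sparse-data method is named; Aim 4 has the same few events.

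*Combined protocol and SAP*

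**What the plan says.** Under Statistical Analyses, item 2 leads with a large-sample test of two proportions and a 95% confidence interval. An exploratory logistic model follows, with baseline vitamin D group as the main predictor and "type of sport and gender as covariates". Item 4 plans exploratory descriptive and inferential statistics, including "the building of logistic regression models, looking for an association between the questionnaire items and the subsequent occurrence of a stress fracture". Item 4 names neither sport nor gender, and it does not say how many questionnaire items there are.

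Neither item names a penalised or exact method, a limit on the number of terms, or a rule for a category without events or a fit that does not converge.

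On size, Local Number of Subjects says: "Tentatively, there will be roughly 200 athletes enrolled in the study". Sample Size Justification takes 10% for the control group and, "if the true reduction in the treated group was to 4% or less", states that "we would have greater than 80% chance (power) in this study".

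**The concern.** Both models use 2015-16 athletes only, so they rest on very few fractures. If a category of a covariate has no event, ordinary maximum likelihood has no finite estimate for that category. Software then prints a huge odds ratio with a meaningless interval, or a convergence warning. With no rule stated in advance, the analyst must decide whether to merge sports, drop terms or change method after seeing where the fractures fell.

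Aim 2's two-proportion comparison is unadjusted, so this model is the only adjusted estimate planned for that aim. In Aim 4 the risk lies in how many questionnaire items enter a model that has so few events.

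**Working it through.** **Plan's own figure.** The power table states "H0: P1-P2=0. H1: P1-P2=D1<>0" and "Test Statistic: Z test with pooled variance", with 200 against 800 athletes and alpha 0.05. At 4% against 10%:

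- Pooled proportion: (200 × 0.04 + 800 × 0.10)/1000 = 0.088.
- Standard error under H0: √[0.088 × 0.912 × (1/200 + 1/800)] = 0.02240.
- Standard error under H1: √[0.04 × 0.96/200 + 0.10 × 0.90/800] = 0.01745.
- Power: Φ[(0.06 − 1.96 × 0.02240)/0.01745] = Φ(0.923) = 0.822.

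This matches the stated 0.8220, so 4% and 10% are the rates the design rests on.

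**Events per slope.** Expected fractures in 2015-16 are 200 × 0.04 = 8 to 200 × 0.10 = 20. Four sports need three indicators. With group and gender that makes five slopes, so there are 8/5 = 1.6 to 20/5 = 4 events per slope. Withdrawal of Subjects leaves withdrawn athletes out of the final analysis, which can only lower these counts. The Aim 1 model has the same covariates but adds about 800 × 0.10 = 80 historical fractures, so this point does not extend to it.

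**Chance of a sport with no fracture.** For sport sizes n_s and a common rate p, the chance is 1 − Π[1 − (1 − p)^n_s]. The documents give no sport sizes, so both rosters below are assumptions. The second has 28 basketball, 55 soccer, 90 track and 27 cross-country athletes.

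| Rate | Fractures | Four sports of 50 | 28/55/90/27 |
|---|---|---|---|
| 4% | 8 | 43% | 60% |
| 6% | 12 | 17% | 36% |
| 8% | 16 | 6% | 20% |
| 10% | 20 | 2% | 11% |

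For example, at 4% with equal sports: 1 − (1 − 0.96^50)^4 = 1 − 0.870^4 = 0.43. Other assumed unequal rosters (track 80-100, cross-country 20-30, soccer 55-60, basketball 25-35) gave 54% to 69% at 4% and 7% to 19% at 10%. Coding the seven teams under Recruitment Methods instead of four sports gave 93% to 96% and 30% to 50%.

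**Whole Aim 2 model.** Simulations of 1,000 datasets per setting assumed 40% of athletes low in vitamin D and half female outside cross-country. At 8 expected events, some coefficient was non-finite in 46% of datasets (equal sports) and 67% (90/20/60/30). At 20 events the figures were 2% and 15%.

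**Vitamin D group odds ratio.** This is infinite when one vitamin D group has no fracture. With 80 low and 120 normal athletes at 4%, the chance is 0.96^80 + 0.96^120 − 0.96^200 = 0.038 + 0.007 − 0.000 = 4.5%; the simulations gave 4% to 5%. At 20 events it was 0.1% or less. The share of low athletes is not in the documents. At 4% the chance is 3% for a 50% share, 9% for 30% and 20% for 20%.

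When the fit was finite, the median standard error of the group log odds ratio was about 0.74 at 8 events and 0.50 at 20. The 95% interval's upper limit is then about 18 and 7 times its lower limit.

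**Bias and remedy.** On the 28/55/90/27 roster at 4%, with a true odds ratio of 2 (log 0.69), ordinary logistic regression was non-finite in about 63% to 64% of datasets. Among finite fits, the mean group log odds ratio was 0.78 to 0.79. Firth regression averaged 0.69 and was finite in 998 of 1,000 datasets.

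**Aim 4.** At 4%, an item endorsed by 10% of 200 athletes has a 0.96^20 = 44% chance of no fracture among endorsers. Inclusion/Exclusion Criteria gives women a separate questionnaire on diet and menstrual cycle. With an assumed 110 women, the chance is 0.96^11 = 64% for a 10% item and 0.96^22 = 41% for a 20% item.

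**The case against.** The strongest reply is that the models are labelled exploratory, and that Aim 2's lead analysis is a two-proportion comparison which does not depend on them. The plan also allows an extra season if data are inadequate. All this stands and limits the consequence. It does not make a non-finite estimate reportable, and the aims as written name only 2015-16.

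The plan does not say that it will use ordinary maximum likelihood or stepwise selection, and Firth is not the only option: exact methods, fewer terms or merged sports would also serve. This is fair, but logistic regression without qualification is normally fitted by maximum likelihood, and none of the alternatives is named.

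A reader might infer four stronger things that the documents do not support:

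- **That the vitamin D odds ratio will often be infinite.** A sport without fractures sends only that sport's own coefficient to infinity; the group effect is still estimated from the other sports.
- **That failure is frequent across the whole range of 8 to 20 fractures.** Near 10%, with four sports and a common rate, it is uncommon.
- **That the sport argument reaches Aim 4.** Item 4 has no sport term, and logistic models are one listed component among descriptive and other inferential statistics.
- **That associations will be badly exaggerated.** The bias found is about 0.1 on the log scale; imprecision is the larger problem.

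**Conclusion.** The point holds at and near the design rate. With about 8 fractures, the Aim 2 model has about 1.6 events per slope and a 43% to 60% chance, on the two main assumed rosters, that at least one sport's odds ratio is not finite. The chance falls to 2% to 11% with 20 fractures. The vitamin D odds ratio is seldom infinite (about 4% to 5% at 8 events if 40% of athletes are low, more if the low group is much smaller), but it is imprecise throughout.

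Aim 4 shares the scarcity of events, against an unstated number of items. The event counts follow from the documents; sport sizes, a common fracture rate across sports, the low-vitamin-D share and the sex mix are assumptions. The effect is on exploratory adjusted estimates, not on the lead comparison. The change is worth making because it is cheap and settles the method before the data are seen.

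**What to change.** In Statistical Analyses, items 2 and 4, state that the logistic models for stress fracture will use Firth penalised likelihood with profile penalised-likelihood 95% confidence intervals. In item 4, add that each model will hold one or very few questionnaire items, with adjustment for sex only where the item was asked of both sexes. Items asked only of women cannot be adjusted for sex.

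The cost is a little more analysis work and slight shrinkage of estimates towards the null. No new data are needed, and the method is in standard software. Firth's method keeps estimates finite but does not supply missing events, so wide intervals should still be expected and reported as such.
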